10.4 Stopping Rules

There are no interim analyses planned that would allow for a determination of futility or overwhelming benefit. Study enrollment will be suspended under the following circumstances:

1. Serious Adverse Events. Study enrollment will be suspended in the event of a single serious adverse event that is determined to be unexpected and at least possibly related. If suspended, study recruitment will not continue until a determination has been made about whether the known risks of participation have changed and the BU Medical Campus/Boston Medical

Center IRB has made a finding that the risk/benefit ratio remains favorable given the possible newly identified risk.

2. Risk of intoxication. Subject recruitment will also be suspended if more than one subject of the first ten subjects enrolled is discontinued by the investigator due to intoxication during the alcohol self administration trial. Due to differences in alcohol tolerance, BAL is not a reliable measure of subjects potentially posing a safety risk. Study staff will make a subjective determination of risk based on the subject's behavior. After 10 subjects have been enrolled, the trial will be suspended if there are more than 10% of subjects whose participation has been halted by the study team due to concerns about physical safety because of intoxication during the alcohol self-administration trial. If suspended for this reason, the study team will consider design changes to reduce the likelihood of this as a potential risk to study subjects. Recruitment would resume when the BU Medical Campus/Boston Medical Center IRB has made a determination that proposed changes to the study design have an acceptable risk/benefit ratio.

11 Data Handling and Record Keeping

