All study procedures will be conducted at the Clinical Studies Unit at Boston Medical Center and the General Clinical Research Unit at Boston University Medical Campus. At the first screening visit a research assistant will greet the prospective subject and provide a copy of the consent form to read prior to meeting with a study physician. After reviewing the consent, candidates will meet with study physician and receive an explanation of the study purpose and requirements. If still interested after receiving an explanation of the study, the candidate will be given an opportunity to review, inquire about, and sign the study informed consent form. A consent questionnaire quiz will be administered to ensure that the subject understands the study procedures. Any incorrect answers will be reviewed until the consenting physician is satisfied that the subject comprehends the misunderstood information. Subjects' BAC will be measured immediately after signing consent to ensure that consent was given while not

The Effects of Exenatide, a GLP-1 Agonist, on Alcohol Self-Administration in Heavy Drinkers
Version 1.8 10.5.20

intoxicated. BAC must be 0.000 when signing the informed consent document. The consenting physician will document the consent process in a progress note in the subject's source binder. Subjects who are deemed to lack decisional capacity will not be enrolled in this study.

B) Protections against Risks

Risks of study medication

To minimize the risk of adverse health events we will instruct subjects to contact study staff with any questions or concerns about changes in health effects after initiating study medication/sham injection. Trained medical staff will evaluate any reported adverse effects and make a clinical determination about continuation in the trial and referral for medical care. Subjects will be given a wallet card that includes a phone number with 24/7 coverage for medical emergencies.

Because of evidence that exenatide can adversely affect fetal development in rats, women will be excluded from study entry if they have a positive urine pregnancy test or if they are of childbearing age and are either not using appropriate methods of contraception or practicing abstinence.

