The effects of the interaction of GLP-1 agonists and alcohol on blood glucose levels has not been adequately studied in humans. The administration of exenatide will decrease plasma glucagon in Type 2 diabetic patients and also may increase insulin release if blood glucose levels are elevated¹³. In fasting elderly Type 2 diabetic patients receiving the antidiabetic sulfonylurea glyburide, alcohol ingestion produced a greater decrease in blood glucose levels than did placebo⁶⁵. Also, ethanol has also been shown to inhibit gluconeogenesis in Type 2 diabetes, although it did not produce alterations in total liver glucose output¹². The consumption of alcohol in healthy subjects receiving the sulfonylurea glipizide did not result in a greater reduction in glucose blood levels than when this drug was taken alone, but did prolong the length of time during these reductions occurred⁶⁶. As a precaution against subjects experiencing hypoglycemia in this study, alcoholic drinks will be administered to subjects with a sugary mixer (e.g. juice, soda). As a protection for the risk of allergic reaction, injections will be performed in the GCRU.

Risks of Phlebotomy

To minimize the risk of pain, bruising, lightheadedness, fainting, and on rare occasions, infection from a blood draw, we will use trained phlebotomists.

Risks of alcohol self-administration

To minimize the risk of subjects reaching a level of intoxication that is uncomfortable to them,

The Effects of Exenatide, a GLP-1 Agonist, on Alcohol Self-Administration in Heavy Drinkers
Version 1.8 10.5.20

we will remind subjects that they can discontinue study participation at any time. Subjects will be monitored during the course of the study, both through direct assessment with study staff and by observation through a video camera in the alcohol laboratory. Medical staff will evaluate subjects and may make a determination to halt study participation if the subject becomes too behaviorally impaired or if there are emergent safety issues. Subjects who have a BAC greater than 0.04 g/dl or who appear to be too behaviorally impaired to leave our research center will be asked to remain in the clinic until their intoxication is reduced to a level that it is safe to discharge them from the research laboratory.

Risk of loss of confidentiality

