Study randomization: Subjects will be randomized to a crossover sequence of drug exposure. Subjects will be assigned to one of two groups, with one group receiving exenatide in the alcohol challenge Trial #1 and the other receiving exenatide prior in the alcohol challenge Trial #2. Randomization of subjects will be accomplished using a stratified randomization procedure that will allow for between-group balance for drinking status (heavy vs. very heavy). Heavy drinking is defined as ≥ 21 and < 35 standard drinks per week for men, and ≥ 14 and < 28 standard drinks per week for women. Very heavy drinking is defined as ≥ 35 standard drinks per week for men, and ≥ 28 standard drinks per week for women. This stratified randomization will minimize the possibility that the order of study drug administration seems to influence outcomes when order effects are actually related to differences in severity of drinking between the two groups of subjects who are receiving the study medication in a different order. On the day of randomization, subjects will undergo an alcohol breath test, urine drug screening, assessment of concomitant medications, and the TLFB. Subjects who have purposefully abstained from drinking and achieved 14 days of abstinence prior to the challenge will be discontinued from participation for ethical reasons⁴⁹.

Alcohol Challenge Trials 1 & 2: Subjects will return to the laboratory within 14 days of the baseline assessment to complete the alcohol Challenge Trial #1. Prior to the visit, subjects will complete a COVID-19 symptom screening questionnaire following standard of care procedures. If the subject does not complete the screening questionnaire before arriving in clinic, study staff will administer the questionnaire outside of the clinic at a 6-foot distance. If the subject answers 'yes' to any question about known COVID symptoms, their in-clinic visit will be cancelled and they will be advised to contact their PCP and/or get tested at a testing center. Concomitant medications, urine drug screening, Blood Alcohol Concentration (BAC) will be assessed to determine eligibility to proceed with the challenge. A BAC reading of 0.000 is required at each visit to continue with the study procedures. For safety reasons, subjects will be asked to arrange transportation plans that does not include driving themselves home.

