There will be a 7-14 day washout period between alcohol Challenge Trial #1 and Trial #2. Based on the known half-life of exenatide, all of the medication will be cleared within 2 days. The washout may extend up to 14 days to provide flexibility in scheduling of Trial #2. After the second alcohol self-administration trial has been completed subjects will receive a copy of the

Figure 2: Alcohol Self-Administration Procedure

Study drug Study drug administered 30 minutes prior to priming dose	Priming Dose 5 minutes Drink mixed to achieve BAC= 0.03g/dl	Absorption 40 minutes BAC measured in 10-minute intervals	Self-Administration Blocks 1 & 2 60 minutes each 4 drinks per block Each drink mixed to raise BAC 0.0125 g/dl
--	---	---	---

The Effects of Exenatide, a GLP-1 Agonist, on Alcohol Self-Administration in Heavy Drinkers
Version 1.8 10.5.20

NIAAA publication *Rethinking Drinking*⁴⁸ and will be encouraged to review rethinking drinking materials online. Subjects will be compensated up to \$448 for completion of all study activities. Subjects will receive a reimbursement of \$50 for the screening visit, \$150 for alcohol Challenge Trial #1, \$150 for alcohol Challenge Trial #2. Subjects will receive a \$50 bonus for completing both alcohol Challenge Trials. Subjects may receive up to \$48 dollars in payments for drinks not consumed during the two alcohol self-administration Trials. Subjects who report no recreational drug use other than marijuana at the time of phone screening but then test positive for recreational drug use other than marijuana at the first in-clinic visit will not be reimbursed. Subjects will be informed of this policy at the time of telephone screening. This measure is in place to prevent subjects from lying about no recreational drug use in order to receive compensation for a single visit in this study.

10 Assessment of Safety and Data Safety Monitoring Plan (DSMP)

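### After a qualifying SAE, section 10.4 as worded suspends only enrollment and recruitment; no text expressly holds injections or alcohol sessions for subjects already enrolled

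*Combined protocol and SAP*

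**What the plan says.** Section 10.4 (Stopping Rules) has one lead-in, which speaks of suspending enrollment, and two limbs.

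- **SAE limb.** "Study enrollment will be suspended in the event of a single serious adverse event", provided the event is unexpected and at least possibly related. After that, "study recruitment will not continue until a determination has been made about whether the known risks of participation have changed", and the IRB must also find that risk/benefit remains favorable.
- **Intoxication limb.** It begins by suspending recruitment. Once ten subjects are enrolled, "the trial will be suspended if there are more than 10% of subjects whose participation has been halted by the study team" over intoxication concerns. It ends by saying when recruitment would resume.

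The design leaves subjects waiting between two exposures. Section 9 states: "There will be a 7-14 day washout period between alcohol Challenge Trial #1 and Trial #2". The two sequences have "one group receiving exenatide in the alcohol challenge Trial #1 and the other receiving exenatide prior in the alcohol challenge Trial #2".

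Other safeguards exist. In section 6.1, medical staff evaluate reported adverse effects and "make a clinical determination about continuation in the trial and referral for medical care". During sessions they "may make a determination to halt study participation if the subject becomes too behaviorally impaired or if there are emergent safety issues". Section 8 lets physicians unblind for medical decisions. Appendix A has eligibility to continue confirmed at each trial visit. Section 10.3 sets IRB reporting limits for Unanticipated Problems: 2 days if fatal or life-threatening, otherwise 7 days. Sections 3.1 and 13 bind the study to institutional policies, federal regulations and ICH GCP.

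**The concern.** The event that triggers the SAE limb is one that might change the known risks of taking part. Those risks arise at the injection and the alcohol session, not at recruitment. A rule that stops new entrants but is silent on subjects between Trial 1 and Trial 2 leaves the people nearest to the next exposure outside its stated scope. For those who had sham first, Trial 2 is their only exenatide dose.

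Section 6.1 acknowledges that the combined effect of GLP-1 agonists and alcohol on blood glucose has not been studied adequately in humans. Section 6.2 says that subjects gain no direct benefit, so a pause takes none from them. At stake is the protection of a small number of subjects over a short period. The validity of the primary analysis is not affected.

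**Working it through.** **Step 1: is a hold stated anywhere?**

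| Provision | What it does | Does it hold Trial 2 until the IRB rules? |
|---|---|---|
| 10.4, SAE limb | Suspends enrollment and recruitment | Not stated |
| 10.4, intoxication limb | Suspends the trial once the 10% limit is passed | Different trigger |
| 6.1, adverse effect review | Clinical decision after a reported effect | Not tied to another subject's SAE |
| 6.1, session monitoring | Staff may halt participation | Discretionary |
| 8, unblinding | Serves medical decisions on subject treatment | No |
| 9 and Appendix A | Pre-session checks, eligibility confirmed per subject | No study-level check listed |
| 10.3 | Sets reporting times | Reporting only |
| 3.1 and 13 | Adopt outside policies | Unknown; the policies are not reproduced |

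No provision expressly imposes the hold.

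**Step 2: can Trial 2 fall due before the IRB rules?** Yes. The washout can be as short as 7 days. The report to the IRB may take up to 7 days for an event that is not fatal or life-threatening, and the ruling comes after the report.

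**Step 3: how many subjects?**

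Inputs:
- 36 randomized (section 12.2).
- Washout W of 7-14 days (section 9).
- Accrual over 12-24 months. This is an assumption: section 2 gives 24 months for the entire study but no accrual period or pattern.
- T, the days from the SAE to the IRB ruling. This is also an assumption, as the documents give no figure.

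With even accrual over D days, subjects pass from Trial 1 to Trial 2 at a rate of 36/D per day. The expected number whose Trial 2 falls due before the ruling is 36 × min(T, W)/D. All 36 are treated as returning for Trial 2, which slightly overstates the count.

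| T | D = 730 days | D = 365 days |
|---|---|---|
| 2 days | 36 × 2/730 = 0.10 | 36 × 2/365 = 0.20 |
| 7 days | 36 × 7/730 = 0.35 | 36 × 7/365 = 0.69 |
| 14 days or more, W = 14 | 36 × 14/730 = 0.69 | 36 × 14/365 = 1.38 |

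Assuming balanced sequences, about half of each figure still has exenatide ahead: 0.05-0.10, 0.17-0.35 and 0.35-0.69. The rest have sham plus alcohol left. All figures are conditional on a qualifying SAE.

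**Step 4: what would a hold cost?**

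The plan's own figure comes first. Section 12.2 states power 0.81 for 28 completers at effect size 0.7 and alpha 0.01. A two-sided paired t-test using the noncentral t distribution gives 0.815, so the figure reproduces.

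- With 27 completers, power is 0.796.
- At 20% non-completion, 36 × 0.80 = 28.8 completers are expected. If every subject held is lost in the worst case above, 28.8 − 1.38 = 27.4.
- At 15% non-completion, 36 × 0.85 = 30.6, and 30.6 − 1.38 = 29.2.

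These counts are before the nausea exclusion in section 12.1.

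A hold could also push screened subjects past their Trial 1 window. Section 9 says: "Subjects will return to the laboratory within 14 days of the baseline assessment to complete the alcohol Challenge Trial #1". If each waits the full 14 days, about 36 × 14/730 = 0.69 to 36 × 14/365 = 1.38 eligible subjects are waiting at any time.

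**The case against.** **The narrow reading is not the only one.** The section is headed as stopping rules, one lead-in covers both limbs, and the intoxication limb moves from recruitment to the trial and back to recruitment. The authors may have used these terms interchangeably. The SAE limb also asks the IRB a study-level question. This stands: the fault is an unstated scope, not a plan to keep dosing.

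**Other rules may fill the gap.** The policies adopted in sections 3.1 and 13 may require a hold. The reporting clocks also shorten the exposure window. A qualifying SAE is already unexpected and possibly related, so it meets two of the three criteria for an Unanticipated Problem in section 10.1, and the third may well follow. The discretion to act on emergent safety issues is not worded as limited to a subject's own event. This stands in part: these provisions reduce the risk, but none states a hold.

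**Physician judgement with prompt reporting is a legitimate design choice.** That is fair, but the SAE limb already makes exposure of new subjects wait for the IRB. It gives no reason to treat pending exposures differently.

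**Three stronger readings are tempting, and the documents do not support them.**
- *The protocol directs sessions to continue after an SAE.* Nothing says so.
- *The different wording of the two limbs proves that the SAE rule was meant to be narrower.* The shared lead-in and the return to recruitment at the end of the intoxication limb undercut that.
- *The harm is everyone between trials: up to 1.38 subjects, with a 75% chance of at least one (1 − exp(−1.38)).* This is an upper bound. It needs a ruling that takes 14 days or more, a 14-day washout for all and 12-month accrual. The harm is limited to those whose Trial 2 falls due before the ruling.

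**Conclusion.** The point holds as a gap in the wording. The SAE limb names only enrollment and recruitment, and no other text expressly holds injections or alcohol sessions for subjects already enrolled. Whether a wider hold was intended, or is required by policies not reproduced in the protocol, cannot be settled from the documents.

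The size is small: fewer than one subject expected for a ruling within 7 days, and at most 0.69-1.38 for a slow one, given a qualifying SAE. This rests on even accrual over 12-24 months and on an assumed turnaround time. No SAE rate is given, so no unconditional probability can be stated with support from the documents. Low severity: a cheap improvement to subject protection that does not bear on the validity of the results.

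**What to change.** Amend the SAE limb of section 10.4 to state that, on a qualifying SAE, enrollment, randomization and all study injections and alcohol challenge sessions, including pending Trial 2 visits, are held until the IRB makes the finding already required. Add that a Trial 2 delayed beyond 14 days by such a hold may be completed once eligibility is reconfirmed, with the delay recorded. The maximum participation lengths in sections 2 and 9 need the same exception.

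The cost is a few sentences of text and, only if the rule triggers, a pause. With late completion allowed, few completers should be lost. If all those held are lost, the average loss is about one completer at most, and a few screened subjects may need rescreening.

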11.1 Confidentiality

All staff will be fully trained in the procedures for protection confidential health information. To maintain subject confidentiality, study data will be coded on CRFs that are identified by a subject number only. Source records with identifying information and CRFs will be stored in double-locked space with access only by authorized staff. Data stored in the REDcap system have strong protections including file encryption and password access. Subject information will not be released without written permission. Upon approval of the study by an IRB, an application will be filed with NIAAA for a Certificate of Confidentiality.

11.2 Source Documents

Source documents in this study include:

Laboratory test results
Photocopies of the urine drug screening test result
ECG tracings
Subject locator form
Subject contact form

Data generated by the methods described in the protocol will be recorded in the subjects' source binder. Data may be transcribed legibly on CRFs for each subject or directly inputted into an electronic system or any combination thereof.

11.3 Case Report Forms

The study case report form (CRF) will be the primary data collection instrument for the study. All data requested on the CRF will be recorded. All missing data will be explained. If a space on the CRF is left blank because the procedure was not done or the question was not asked, a written explanation will be included to detail why the data was not recorded. If the item is not applicable to the individual case, a notation will be made. All entries on will be printed legibly in black ink.

The Effects of Exenatide, a GLP-1 Agonist, on Alcohol Self-Administration in Heavy Drinkers
Version 1.8 10.5.20

If any entry error has been made, to correct such an error, a single straight line will be drawn through the incorrect entry and the correct data will be entered closely to the original data. All such changes will be initialed and dated. There will be no erasures or white-out on CRFs. For clarification of illegible or uncertain entries, the clarification will be printed near the item, then initialed and dated. Electronic CRFs in the REDcap system will include an audit trail.

The CRFs that will be used in this study are:

Demographics
Concomitant Medications
Adverse Events
Birth Control Assessment
Urine Drug Screening
Vital Signs
Blood Alcohol Level
Laboratory summary sheet
Time-line Follow-back
Pregnancy test
Birth control assessment
Medical History
Blood Glucose
Nausea VAS
Physical Examination
MINI diagnoses summary
Medication Compliance log
Eligibility
ECG
C-SSRS
CIWA-AR
OCDS
AUQ
VAS

11.4 Study Records Retention

Study records will be retained for at least seven years after completion of the study.

12 Statistical Plan

12.1 Study Hypotheses and Planned Analyses

For our primary outcomes, data from subjects who experience moderate to severe nausea during the alcohol self-administration trials will be excluded from our statistical analysis. Although the dosing chosen for this study minimizes the potential for nausea as a medication side effect, this may occur in some subjects. These subjects will be excluded from analyses as medication-induced nausea could confound the drinking outcomes. The presence of nausea will be established by a rating greater than 30 on a VAS scale that rates nausea from no nausea to unbearable nausea⁵³.

Hypothesis	Proposed Analyses
1. Subjects will consume less alcohol during an alcohol Challenge Trial when receiving exenatide	The volume of alcohol consumed during alcohol challenge trials 1 and 2 will be used to test the effect of exenatide on alcohol consumption. We will use a mixed

The Effects of Exenatide, a GLP-1 Agonist, on Alcohol Self-Administration in Heavy Drinkers
 Version 1.8 10.5.20

compared to when they receive a sham injection.	models repeated measures approach to test for differences between alcohol consumption between the exenatide and sham injection self-administration trials ⁵⁴⁻⁵⁵ . This data will be divided into first and second-hour blocks of self-administration. Within-subject factors for this analysis will include Treatment and Time Block. Trial order will be used as covariate in these analyses to allow evaluation as to whether the order of treatments had a significant effect on the outcome. Appropriate covariance structures will be determined using Akaike's information criteria to evaluate the best model fit. Results analysis will be examined for both treatment effects and the Treatment x Time Block interaction results.
2. Subjects will report lower levels of craving as measured by the Visual Analog Scale (VAS) and the Alcohol Urge questionnaire (AUQ) during the exenatide Challenge Trial compared to the sham injection Challenge Trial.	Craving measures (AUQ and VAS) collected at 30-minute intervals during the self-administration trials will be used to test the effect of exenatide on alcohol craving. A mixed models approach will be used to test for differences in craving between the exenatide and sham injection Challenge Trials. Within-subject factors for this analysis will include Treatment and Time Block. Trial order will be used as covariate in these analyses to allow evaluation as to whether the order of treatments has a significant effect on the outcome.
Hypothesis 3: Areas under the breath alcohol concentration curves (AUC's) in heavy drinkers obtained during the first 40 minutes after ingestion of the priming drink of alcohol will be significantly lower in subjects when they receive exenatide as compared to when they are given sham injections	AUC's for BAC obtained using data obtained during the 40-minute absorption period will be compared between Challenge Trials using a repeated measures mixed models approach. In addition, individual BAC values obtained at 10-minute intervals after alcohol ingestion of the priming drink also will be compared between the sham injection and exenatide treatment trials using a repeated measures mixed models approach. A significant time x trial interaction value also will be taken to indicate a significant between trial difference in the rates of alcohol absorption.
Hypothesis 4. The proportion of subjects with post-trial blood glucose levels in the hypoglycemic range will not differ significantly between the sham injection and exenatide trials.	The proportion of subjects with blood glucose values below 50 mg/dl will be compared within subjects using the McNemar's test. We hypothesize that there will be no difference in blood glucose levels between the alcohol Challenge Trials.

